4. RANDOMIZATION AND BLINDING

4.1 Method of Group Assignment and Randomization

Subjects will be enrolled in a stepwise dosage-escalation manner into one of three cohorts:

- Cohort 1: low dosage of RSV F subunit vaccine [45 µg],
- Cohort 2: middle dosage of RSV F subunit vaccine [90 µg], and
- Cohort 3: high dosage of RSV F subunit vaccine [135 µg]).

Within each cohort, subjects will be randomly allocated (1:1:1:1) to receive vaccine with no adjuvant, vaccine with aluminum hydroxide, vaccine with MF59, or placebo, as outlined in [Table 4.1](#). All subjects will receive two doses of a 0.5 mL intramuscular injection of the vaccine with adjuvant (aluminum hydroxide [1 mg] or MF59 [0.25 mL; 9.75 mg squalene and surfactants]), the vaccine without adjuvant, or saline placebo. There will be approximately 24 subjects in each active treatment group, and 24 placebo subjects in each cohort.

Table 4.1.

Cohort	Dosage	Route of Administration	Regimen: Two Doses †		
			No Adjuvant	Al(OH) ₃ ‡	MF59 ‡
1	45 µg	IM (0.5 mL)	24	24	24
	Placebo (saline)	IM (0.5 mL)	24		
2	90 µg	IM (0.5 mL)	24	24	24
	Placebo (saline)	IM (0.5 mL)	24		
3	135 µg	IM (0.5 mL)	24	24	24
	Placebo (saline)	IM (0.5 mL)	24		

For further details please refer to [section 5.1. of the protocol](#).

4.1.1 Definition of Vaccination Errors

The list below provides some examples of potential errors that may occur during vaccination:

- Subjects got vaccinated with a vaccine different from the one assigned at randomization

- Subjects got vaccinated with the correct vaccine but containing a lower volume
- Subjects got vaccinated with different vaccine at the second dose.

Please see [Section 7](#) a complete guidance on how vaccination errors are handled in the statistical analysis.

4.2 Blinding and Unblinding

For details please refer to [section 3.3 of the protocol](#).

If a subject is unblinded during the study, it is to be reported as a major protocol deviation, except for Pharmacovigilance unblinded suspected unexpected serious adverse reactions (SUSAR). The unblinding will be documented appropriately (for details see SOP BCDM-04).

The first-line analysis excludes unblinded subject(s) in immunogenicity or efficacy statistical analyses based on the per-protocol set. The unblinded subjects will be included in the full analysis set (FAS) and safety sets.

Further details on measures taken to ensure blinding can be found in the study-specific Data Security Plan.

5. **SAMPLE SIZE AND POWER CONSIDERATIONS**

For details please refer to [section 7.4.2.4 of the protocol](#).

Sample size/power considerations are included in the study protocol. Technical details including statistical assumptions and software are given in a separate sample size memo authored by the study Biostatistician. In the same document, a statistical co-reviewer verified and documented the sample size/power considerations. This document was completed prior to finalization of the protocol and stored in

PPD

6. DETERMINATION OF PROTOCOL DEVIATIONS

6.1 Definition of Protocol Deviations

Clinical Study Report (CSR) reportable protocol deviations (PDs) are defined in accordance with ICH E3 as important PDs related to study inclusion or exclusion criteria, conduct of the trial, subject management or subject assessment resulting in the potential to jeopardize the safety or rights of the trial subjects or the scientific value of the trial.

All reportable PDs will be evaluated before unblinding and classified according to ICH into the following five categories:

- Subject developed withdrawal criteria during the study but was not withdrawn
 - Underlying medical condition forbidden by the protocol or which may influence immune response.
 - Subject had contraindication for a subsequent study vaccination but was vaccinated.
 - Concomitant infection related to the vaccine which may influence immune response.
- Subject received wrong vaccine or incorrect dose
 - Study vaccine was not administered at all
 - Vaccine administration not according to protocol.
 - Randomization failure.
- Subject took an excluded concomitant medication
 - Administration of concomitant vaccine(s) forbidden in the protocol.
 - Administration of any medication forbidden by the protocol.
- Subject randomized and did not satisfy the entry criteria
 - Subject did not meet entry criteria.
- Key study procedures missed or performed out of window
 - Randomization code was broken.
 - Subject did not comply with study vaccination schedule.
 - Subject did not provide any post-vaccination safety data.
 - Subject did not comply with blood draw schedule.
 - Serological results not available post-vaccination.

- Obvious incoherence or error in data.

CSR reportable PD will lead to exclusion of the subject or part of the subject's data from at least one analysis set.

The number of subjects in any and by PD category will be summarized by vaccine and overall and individual subject listings will be provided in an appendix.

Prior to unblinding, designated GSK staff will develop a memo that describes the PDs that lead to exclusions from analysis sets. This memo will be signed off by at least the Biostatistician and the Cluster Physician and will be included in the trial master file (Exclusion Memo).

Prematurely terminating study participation for reasons such as withdrawal of consent or occurrence of adverse events (including death) is not considered as a PD. The missing assessments that should have otherwise been collected for that subject later in the study are also not considered as a PD.

Comments:

- Missed safety calls are not considered reportable protocol deviations.
- Implausible measurements do not lead to PD.

6.2 Determination of Protocol Deviations

Prior to unblinding, a set of listings will be provided to the Clinical Research and Development Lead (CRDL) and the Study Delivery Lead (SDL) for review according to SOP MON-11.

The listings will be programmed following the list presented in table in [section 7.8](#), and specifically using the PD codes specified in the first column.

After the review, the CRDL and the SDL will provide the Biostatistician with:

- An assessment of CSR reportable PD based on blinded clinical data review.
- An assessment of subjects without PD (e.g., premature withdrawals due to adverse event, withdrawal of consent) who should be excluded from an analysis set.

6.3 Exclusions of Individual Values for Safety Analysis

Some local and systemic adverse events will be directly measured by the subject and will not be subject to a reconciliation process, even if they are biologically implausible.

Therefore these implausible measurements will be removed from the analysis but included in listings. Implausible measurements are summarized in the table below:

Table 6.3-1: Implausible Solicited Adverse Events

Parameter	Implausible measurements
Body temperature	$\leq 33^{\circ}\text{C}$ or $\geq 42^{\circ}\text{C}$
Erythema	Values ≥ 900 mm Measurements < 0 mm
Induration	Values ≥ 500 mm Measurements < 0 mm
Swelling	Values ≥ 500 mm Measurements < 0 mm

7. ANALYSIS SETS

7.1 All Enrolled Set

All screened subjects who provide informed consent and provide demographic and/or other baseline screening measurements, regardless of the subject's randomization and vaccination status in the trial, and receive a subject ID.

Demography and baseline characteristics tables as well as subject listings will be produced on the All Enrolled Set.

7.2 Exposed Set

All subjects in the All Enrolled Set who receive a study vaccination.

7.3 Full Analysis Set (FAS) Immunogenicity Set

All subjects in the All Enrolled Set who are randomized, receive at least one study vaccination and

For primary immunogenicity endpoints:

- Provide immunogenicity data for anti-RSV NAb at day 57 (FAS 9).
- Provide immunogenicity data for anti-RSV NAb at baseline and day 57 (FAS 1-9).

In case of vaccination error, subjects in the FAS will be analyzed "as randomized" (i.e., according to the vaccine a subject was designated to receive, which may be different from the vaccine the subject actually received).

If a subject is unblinded during the study, he/she will be included in the FAS.

7.4 Per Protocol Set (PPS), Immunogenicity Set

All subjects in the FAS Immunogenicity who:

- Correctly receive the vaccine (i.e., receive the vaccine to which the subject is randomized and at the scheduled time points).
- Have no major protocol deviations leading to exclusion (see [section 6.2](#)) as defined prior to unblinding / analysis.
- Are not excluded due to other reasons defined prior to unblinding or analysis (see [section 6.2](#))

In detail:

For primary immunogenicity endpoints:

- Provide immunogenicity data for anti-RSV NAb at day 57 (PPS 9).
- Provide immunogenicity data for anti-RSV NAb at baseline and day 57 (PPS 1-9).

For secondary immunogenicity endpoints:

- Provide immunogenicity data for anti-RSV NAb at day 29 (PPS 5).
- Provide immunogenicity data for anti-RSV NAb at day 181 (PPS 12).
- Provide immunogenicity data for anti-RSV NAb at baseline and day 29 (PPS 1-5).
- Provide immunogenicity data for anti-RSV NAb at baseline and day 181 (PPS 1-12).
- Provide immunogenicity data for RSV proteins F, G and N at baseline (PPS 1)
- Provide immunogenicity data for RSV proteins F, G and N at day 29 (PPS 5)
- Provide immunogenicity data for RSV proteins F, G and N at day 57 (PPS 9)
- Provide immunogenicity data for RSV proteins F, G and N at day 181 (PPS 12)

In case of vaccination error, the subject is excluded from the PPS. If a subject receives a vaccine, labelled for another subject but the same as the one the subject was randomized to, the subject will not be removed from the PPS.

A minimum of 4-fold increase in antibody titers against RSV N or G from baseline to post vaccination will be considered indicative of possible natural RSV infection. This will be considered a CSR-reportable protocol deviation leading to exclusion from the PPS with associated code 250 “Concomitant infection which may influence vaccine-specific immune responses”.

If a subject is unblinded during the study, except for SUSAR, he/she will be excluded from all PPS analyses.

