240	Underlying medical condition forbidden by the protocol					EXC	EXC	EXC	EXC	EXC	EXC
250	Concomitant infection related to the vaccine which may influence immune response					EXC	EXC	EXC	EXC	EXC	EXC
260.1	Did not comply with study vaccination schedule	Dose 1				EXC	EXC	EXC	EXC	EXC	EXC
260.x	Did not comply with study vaccination schedule	Dose 2					EXC	EXC		EXC	EXC
270	Did not comply with blood draw schedule					EXC	EXC	EXC	EXC	EXC	EXC

PD code	PD Description	Study Objective/ Period	FAS 1	FAS x	FAS 1x	PPS 1	PPS x	PPS 1x	EXP 1	EXP x	EXP 1x
	Exclusion code		FAS1FL	FASxFL	FAS1xFL	PPS1FL	PPSxFL	PPS1xFL	EXP1FL	EXPxFL	EXP1xFL
280	Subject who developed withdrawal criteria but was not withdrawn	Visit x					EXC	EXC		EXC	EXC
290	Early withdrawal	Visit x		EXC	EXC		EXC	EXC		EXC	EXC

*except from PPS 5 as deviation would occur after blood draw for day 29 assessment.

FAS = Full Analysis Set; PPS=Per Protocol Set; EXP=Exploratory Immunogenicity Set, EXC = excluded from this analysis set.

FAS 1, PPS 1, and EXP 1 refer to any immunogenicity analyses including values for baseline.

FAS x, PPS x, and EXP x refer to any immunogenicity analyses including values for visit x (i.e. visits after V1 with immunogenicity evaluation).

FAS 1x, PPS 1x, and EXP 1x refer to any immunogenicity analyses including values for baseline and visit x.

Code 999 is not a protocol deviation but it will lead to exclusion.

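### SAP sections 7.3/7.4 and Table 7.8-2 conflict on who enters the Day 29 and Day 181 per-protocol sets, and row 140.4 spares one-dose subjects in PPS 5 but not in PPS 1-5

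*SAP*

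**What the plan says.** Section numbers are those of the last SAP version in the file.

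- **Section 7.3 (FAS).** The definition opens with "All subjects in the All Enrolled Set who are randomized, receive at least one study vaccination and", and the sentence is completed under the heading "For primary immunogenicity endpoints" by two conditions: "Provide immunogenicity data for anti-RSV NAb at day 57 (FAS 9") and "Provide immunogenicity data for anti-RSV NAb at baseline and day 57 (FAS 1-9"). No FAS is given for Day 29, for Day 181, or for proteins F, G and N, and there is no clause for secondary endpoints.
- **Section 7.4 (PPS).** All sets are drawn from "All subjects in the FAS Immunogenicity who" also received the correct vaccine at the scheduled times and had no excluding deviation. Under a separate secondary-endpoint heading it lists "Provide immunogenicity data for anti-RSV NAb at day 29 (PPS 5"), "Provide immunogenicity data for anti-RSV NAb at day 181 (PPS 12"), the paired sets 1-5 and 1-12, and the F/G/N sets at four visits.
- **Table 7.8-2.** FAS x and PPS x are defined visit by visit. Code 110.x (no serology result at visit x) excludes only from the x and 1x sets of that visit. Code 140.4 (first dose only) excludes from PPS x with an asterisk and from PPS 1x without one. The footnote reads "except from PPS 5 as deviation would occur after blood draw for day 29 assessment".
- **Section 8.2.2.** The primary analysis is repeated on the FAS. The secondary immunogenicity analyses use the PPS only.

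**The concern.** The text and the table give different answers to a basic question: does a subject need a Day 57 NAb result to be analyzed at Day 29 or Day 181? Under the literal text, yes, and for every antigen. F, G and N results at any visit would depend on a NAb result from another assay at Day 57. Under the table, no.

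Making Day 29 membership depend on a later sample discards valid data and selects on an event after the measurement. It also runs against the table footnote, which holds that what happens after the Day 29 draw should not remove a subject from Day 29. Because the secondary analyses have no FAS repeat, the reported results would not show which rule had been programmed.

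Row 140.4 has a problem of its own, whichever rule governs. Its exemption reaches the set with the Day 29 result alone, but not the set with baseline and Day 29, which the ANCOVA and the 4-fold endpoint need.

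**Working it through.** The SAP gives no figure that bears on this point (section 5 refers sample size to the protocol), so there is nothing to reproduce. The check compares set membership under the two rules.

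**1. Availability patterns.** Take a vaccinated subject with no other deviation. NAb results at Days 1, 29, 57 and 181 are each present or absent, giving 2^4 = 16 patterns. Compare membership of PPS 5, 12, 1-5 and 1-12.

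- Literal text: member if Day 57 is present and the set's own visit(s) are present.
- Table, code 110: member if the set's own visit(s) are present.

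The 8 patterns with Day 57 present agree. Of the 8 without it, the 2 that also lack both Day 29 and Day 181 agree. The other 6 differ:

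| Day 1 | Day 29 | Day 57 | Day 181 | Literal text | Table 7.8-2 |
|---|---|---|---|---|---|
| yes | yes | no | yes | none | 5, 12, 1-5, 1-12 |
| yes | yes | no | no | none | 5, 1-5 |
| yes | no | no | yes | none | 12, 1-12 |
| no | yes | no | yes | none | 5, 12 |
| no | yes | no | no | none | 5 |
| no | no | no | yes | none | 12 |

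If each PPS is drawn from the FAS of its own visit, all 6 agree.

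**2. One-dose subject with Day 1 and Day 29 results.**

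- Section 7.4 text: fails the requirement to receive vaccine at the scheduled time points, so is out of every PPS.
- Table row 140.4: in PPS 5 (asterisk), out of PPS 1-5 (no asterisk).
- Use: the table notes define 1x sets as those for analyses with baseline and visit x values. Sections 8.1, 11.2 and 11.3 adjust Day 29 titers for baseline, and the 4-fold endpoint is a rise from baseline. Both therefore use PPS 1-5.

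The subject counts in the unadjusted Day 29 GMT but not in the adjusted GMT or the 4-fold proportion. Yet the deviation follows the Day 29 draw in both cases.

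**3. Size at Day 29 (illustration).** Group size 24 and total 288 are from sections 3 and 4.1. The share m without a Day 57 result is not in the SAP; take m = 5% to 15%, all with usable Day 29 data.

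- Per group: 24 × 0.05 = 1.2 to 24 × 0.15 = 3.6.
- Overall: 288 × 0.05 = 14.4 to 288 × 0.15 = 43.2.
- CI width factor, 1/√(1 − m): 1/√0.95 = 1.026 to 1/√0.85 = 1.085.
- Chance that a given group loses at least one subject, 1 − (1 − m)^24: 71% to 98%. At m = 2% it is 38%, with 0.5 subjects expected.

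**The case against.** The strongest reply is that section 7.3 places both Day 57 conditions under the primary-endpoint heading, while 7.4 has its own secondary-endpoint list. Read in parallel, the FAS behind the secondary sets is simply randomized and vaccinated. Since the FAS is used only for the primary analysis, it is understandable that 7.3 lists only Day 57 sets. Section 6.2 also has the deviation listings programmed from the section 7.8 table, so a programmer working from its codes would probably keep these subjects.

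This stands as far as it goes. A reader might infer that the plan definitely drops everyone without a Day 57 result from all secondary analyses. The documents do not support that: it follows only from the literal text. But 7.3 has no secondary clause, so the lenient reading has to be supplied, and no sentence gives the table precedence for set membership.

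Other limits also stand:

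- One-dose subjects need not lack Day 57 data. Note r to Table 3-1 recommends Visit 9 procedures for those who terminate before that visit.
- For one-dose subjects, part of the tension comes from the scheduled-time-points condition in 7.4 rather than from the FAS nesting.
- A missed Day 57 draw coded 270 (blood-draw schedule) would remove the subject from every PPS under both rules.
- At Day 181, one-dose subjects are already out of PPS 12 under code 140.4, and early withdrawals generally have no sample.
- The tests are descriptive (section 8.4), and under the SAP's own missing-completely-at-random assumption the cost is precision, not bias.

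None of this answers the row 140.4 point, which arises within the table itself.

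**Conclusion.** The SAP is internally inconsistent on membership of the Day 29 and Day 181 per-protocol sets. On a literal reading of 7.3 and 7.4, subjects with valid data at those visits but no Day 57 NAb result could be excluded; under Table 7.8-2 they stay. The firmest part is row 140.4, which as written removes one-dose subjects from the baseline-adjusted Day 29 ANCOVA and the Day 29 4-fold endpoint for no reason the footnote supports.

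The primary Day 57 NAb analysis is unaffected. The actual loss is unknown. At an assumed 5% to 15% without Day 57 data it is at most about 1 to 4 of 24 per group at Day 29, with CIs up to 3% to 8% wider. That upper bound assumes that every such subject has usable Day 29 data and no other exclusion. It should not be carried over to Day 181, where the loss is smaller. The number of one-dose subjects cannot be estimated from the SAP.

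**What to change.** 1. In 7.3, state that the base FAS is all randomized subjects with at least one study vaccination, and keep the Day 57 conditions as those of FAS 9 and FAS 1-9 only.
2. In 7.4, state that each PPS x or 1-x is drawn from the FAS x or 1-x of the same visit and antigen, as in Table 7.8-2.
3. Align the scheduled-time-points condition in 7.4 with the footnote for Day 29, so that text and table treat one-dose subjects alike.
4. In row 140.4, extend the asterisk to PPS 1-5 and name that set in the footnote. The EXP columns of the row show the same pattern and can be settled at the same time.

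The cost is SAP wording and analysis-set flags. No new data or additional analyses are needed.

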8.2.2 Immunogenicity Data

Missing immunogenicity values are considered missing completely at random (MCAR) and therefore will not contain information that impact the result of the analysis (i.e., not informative). Imputation methods will therefore not be used.

Population of analyses:

PPS will be considered the principal analysis set. The primary immunogenicity analyses will be conducted on the PPS and will be repeated using the FAS as a measure of robustness. All other primary and secondary immunogenicity analyses will be based on the PPS.

The exploratory immunogenicity analyses will be based on the EXP.

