11.3 Secondary Objectives Analysis

Serum anti-RSV NAb titer

Secondary immunogenicity endpoints are:

1. GMT of the serum anti-RSV NAb titer at Day 1 (baseline), Day 29 (28 days after the first dose), and Day 181 (six months after the first dose).
2. Proportion of subjects with a ≥ 4 -fold increase in serum anti-RSV NAb titer from Day 1 (baseline) to all other time points (Day 29 [28 days after the first dose] and Day 181 [six months after the first dose]).
3. Proportion of subjects at Day 29 (28 days after the first dose), Day 57 (28 days after the second dose), and Day 181 (six months after the first dose) who achieve serum anti-RSV NAb titers greater than the 3rd quartile of the serum anti-RSV NAb titers overall distribution at Day 1 (baseline).
4. Reverse cumulative distribution of serum anti-RSV NAb titers at Day 1 (baseline), Day 29 (28 days after the first dose), Day 57 (28 days after the second dose), and Day 181 (six months after the first dose).

The same statistical model as the one used for the primary objectives will be applied to evaluate the serum neutralizing antibody response at Day 1, Day 29 and Day 181. No test for interaction will be conducted for the GMT analyses.

Proportions of subjects with a ≥ 4 -fold increase in serum anti-RSV NAb titer from baseline will also be presented for each treatment group within each cohort together with their two-sided 95% Clopper-Pearson CIs. Additionally, the proportions of subjects whose serum anti-RSV NAb titer at Day 29, Day 57 and Day 181 greater than the third quartile (75-th percentile) of the serum anti-RSV NAb titer at Day 1 for all subjects combined will be presented for each treatment group within each cohort, together with their two-sided 95% CIs.

Reverse Cumulative Distribution Functions (RCDFs) will be produced.

Serum total binding antibody responses

Secondary immunogenicity endpoints are:

1. GMT of the serum total binding antibody to each of the RSV proteins F, G, and N at Day 1 (baseline), Day 29 (28 days after the first dose), Day 57 (28 days after the second dose), and Day 181 (six months after the first dose).
2. Proportion of subjects with a ≥ 4 -fold increase in serum total binding antibody titers to each of the RSV proteins F, G, and N from Day 1 (baseline) to all time points (Day 29 [28 days after the first dose], Day 57 [28 days after the second dose], and Day 181 [six months after the first dose]).

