3. Proportion of subjects at Days 29 (28 days after the first dose), Day 57 (28 days after the second dose), and Day 181 (six months after the first dose) who achieve serum total binding antibody titers to each of the RSV proteins F, G, and N greater than the 3rd quartile of serum total binding antibody titers to RSV protein F at Day 1 (baseline).
4. Reverse cumulative distribution of serum total binding antibody to each of the RSV proteins F, G, and N at Day 1 (baseline), Day 29 (28 days after the first dose), Day 57 (28 days after the second dose), and Day 181 (six months after the first dose).

Analyses of the serum total binding antibody responses to each of the RSV proteins, F, G, and N will use the same primary ANCOVA model as for the primary objective. Similarly, the proportions of subjects with a ≥ 4 -fold increase in serum total binding antibody titers will be analyzed in the same manner as the anti-RSV NAb titers. Additionally, the third quartile of the serum total binding antibody to each of the RSV proteins at Day 1 for all subject combined will be determined; and, the proportions of

subjects with a post-vaccination titer greater than or equal to that value will be analyzed in the same manner as the 4-fold increase analyses.

Ratio of serum NAb titer to serum total binding antibody titers

1. Ratio of RSV F subunit serum neutralizing antibody (NAb) titer to each of the RSV F subunit serum total binding antibody titers to RSV proteins F, G, and N at Day 1 (baseline), Day 29 (28 days after the first dose), Day 57 (28 days after the second dose), and Day 181 (six months after the first dose).

Analyses of the ratio of serum NAb titer to serum total binding antibody titer to each of the RSV proteins (F, G, and N) will use the same primary ANCOVA model as for the primary objective with the serum NAb titer at Day 1 as the covariate.

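### The 4-fold anti-G and anti-N responder rates are analysed on a set that excludes every 4-fold anti-G or anti-N responder, so on any natural reading they can only be 0/n

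*SAP*

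**What the plan says.** Section numbers refer to the latest SAP text, in which the analysis-set overview is Table 7.8-2.

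- **Exclusion rule (7.4).** The trigger is "A minimum of 4-fold increase in antibody titers against RSV N or G from baseline to post vaccination". The consequence follows at once: "This will be considered a CSR-reportable protocol deviation leading to exclusion from the PPS with associated code 250". No visit is named.
- **Table 7.8-2.** Code 250 ("Concomitant infection related to the vaccine which may influence immune response") is marked as an exclusion for PPS 1, PPS x and PPS 1x. It is not marked for any Full Analysis Set (FAS) column, and its period cell is blank.
- **Endpoint (11.3, serum total binding antibody, item 2).** The proportion of subjects with a rise of at least 4-fold is described as an "increase in serum total binding antibody titers to each of the RSV proteins F, G, and N from Day 1 (baseline) to all time points", namely Days 29, 57 and 181. It "will be analyzed in the same manner as the anti-RSV NAb titers", that is, as a proportion with a two-sided 95% Clopper-Pearson interval for each treatment group within each cohort.
- **Threshold (8.7).** A responder has a ratio to pre-vaccination at or above 4.
- **Analysis set (8.2.2).** The primary immunogenicity analyses are run on the PPS and repeated on the FAS. For the rest: "All other primary and secondary immunogenicity analyses will be based on the PPS".
- **FAS (7.3).** It is defined only through NAb data at Day 57, alone or with baseline. No FAS is defined for binding antibody to G or N.

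**The concern.** The exclusion in 7.4 and the endpoint in 11.3 use the same assay results, the same baseline and the same 4-fold cut. A subject who would count as a G or N responder is by that fact outside the population in which responders are counted. The resulting tables would show zero in every group, placebo included, whether or not anyone seroresponded.

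A reader of those tables could take the zeros as a finding that no subject had a G or N response, and so that no natural infection occurred during follow-up. Because the SAP itself treats such rises as a marker of infection, that is the main thing these two rates could show, and it is what has been removed.

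**Working it through.** The SAP gives no expected G or N responder rate, so there is no figure of its own to reproduce. The check is set logic followed by short arithmetic.

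**Step 1: numerator.** Let E be the event of a rise of at least 4-fold in anti-G or anti-N after vaccination. Under 7.4, the PPS excludes E. The G responder event and the N responder event are each contained in E, because both use a cut of at least 4 from baseline. Within the PPS the numerator is therefore 0.

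**Step 2: does this depend on how *post vaccination* is read?**

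| Reading of the trigger | G and N responder rates on the PPS |
|---|---|
| Any post-vaccination visit | 0 at Days 29, 57 and 181 |
| The visit being analysed | 0 at Days 29, 57 and 181 |
| Any visit up to the one analysed | 0 at Days 29, 57 and 181 |
| Day 57 only (not stated in the SAP) | 0 at Day 57; other visits can be above 0 |

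The first reading fits Table 7.8-2 best, since even the baseline set PPS 1 is excluded.

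A simulation (96,000 subjects per scenario) confirmed the table. Its assumptions are not from the SAP: an infection risk of 2%, 5% or 10% per between-visit interval; a rise after infection averaging 0.9 log10 (SD 0.25); background variation with SD 0.12 log10.

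- With no code-250 exclusion, the responder rates were about 1.7% to 8.5% at Day 29, 3.4% to 16% at Day 57 and 5% to 23% at Day 181.
- Under each of the first three readings they were exactly 0.
- Under the Day-57-only reading, Day 181 was about 1.7% to 8.7% and Day 29 was below 0.1%.

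**Step 3: number of affected results.** Three cohorts × four groups = 12 groups of about 24 (12 × 24 = 288, the planned total). 2 antigens × 3 visits × 12 groups = 72 proportions.

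**Step 4: the interval.** For 0/n the Clopper-Pearson upper limit is 1 − 0.025^(1/n).

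- n = 24: 1 − 0.025^(1/24) = 14.2%. For these rates this arises only if nobody in the group was excluded, and then 0/24 is simply the correct observation.
- n = 18: 1 − 0.025^(1/18) = 18.5%. This arises if 6 of 24 were excluded under code 250.

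If those six all rose at least 4-fold on one antigen at one visit, the observed rate among the 24 would be 6/24 = 25%. The table would show 0/18 with an interval of 0% to 18.5%, which lies wholly below 25%.

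**Step 5: the other G and N summaries.** The GMTs, the proportions above the baseline third quartile, the reverse cumulative curves and the NAb/G and NAb/N ratios lose the same subjects. They are truncated on their own outcome, but no value is fixed in advance.

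**The case against.** Several counter-arguments have weight.

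- **The trigger visit is unspecified.** If it were one visit only, the rates at other visits could be above 0. That is true, and the conclusion has to be stated with this condition. Neither 7.4 nor Table 7.8-2 supports the restriction, and the rate at the trigger visit itself would still be 0.
- **The excluded subjects are not hidden.** Section 6.1 plans a summary of deviations by category and individual listings, and 9.1 gives the size of each analysis set. So the infected subjects do not vanish from the report, as a reader might infer. The category that holds concomitant infection also holds underlying conditions and contraindications, however, so no count by code, antigen or visit is planned.
- **The remaining G and N summaries may be meant for uninfected subjects.** The vaccine contains only F, and describing NAb/G and NAb/N ratios without natural infection is a coherent per-protocol aim. This stands. It is tempting to call every G and N result invalid, but the SAP supports that only for the two responder rates.
- **A wholesale move to the FAS is more than is needed.** The FAS also readmits subjects with wrong-vaccine, entry-criteria, forbidden-medication and schedule deviations. This stands too and shapes the fix.
- **The stakes are limited.** These are descriptive secondary endpoints for two antigens that are not in the vaccine, in a Phase 1 study that uses tests only descriptively (8.4).

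**Conclusion.** The contradiction is real and the text is wrong as written. With code 250 applied at any visit, at the visit analysed, or at visits up to it, all 72 G and N responder proportions are 0/n. Their confidence limits depend only on how many subjects remain and say nothing about the true rate. The one assumption is that *post vaccination* does not mean a single visit. No assumption about infection rates is needed.

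Three stronger readings are not supported. The upper limit is not 14.2% whatever the true rate, because excluded subjects leave the denominator. The other G and N summaries are selected but not forced. The primary Day 57 NAb analyses and the anti-F responder rate are not forced to any value, and the primary analyses are repeated on the FAS, where code 250 does not apply. This should be fixed before the secondary tables are produced, but it does not threaten the primary objective.

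**What to change.** 1. Analyse the anti-G and anti-N responder rates at Days 29, 57 and 181 on a set that does not apply code 250. Either define a PPS variant without code 250 (baseline plus visit x), which keeps the other per-protocol exclusions, or use FAS 1x and extend 7.3 to binding antibody at each visit. Amend 8.2.2 to match.
2. Keep code 250 for the NAb and anti-F analyses on the PPS.
3. State in 7.4, and in the blank period cell of Table 7.8-2, which visits trigger code 250.
4. Report the number of code-250 subjects by group and visit.
5. For the G and N GMTs, third-quartile proportions, reverse cumulative curves and NAb/G and NAb/N ratios, add a sensitivity analysis on the same code-250-free set, or footnote the exclusion on each table and figure.

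The cost is SAP wording, one population flag on tables already planned, one small count table and, if chosen, repeat runs of existing programs. No new data are needed. FAS flags without the code-250 exclusion already exist in Table 7.8-2.
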